9.4 N/A

10.0 Vulnerable Populations

10.1 N/A

11.0 Local Number of Subjects

11.1 We aim to complete treatment with and obtain post-treatment assessment data from a total of 30 participants (15 in TMH and 15 in VR group). We will enroll up to 60 participants in the trial as needed to account for screen fails, withdrawals, and drops.

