1.0 Study Summary

1.1

Study Title	Doxy.me VR vs. Telemental Health-Based Exposure Therapy
Study Design	Feasibility randomized controlled efficacy trial
Primary Objective/Purpose	Assess the feasibility of conducting a randomized controlled efficacy trial comparing the delivery of exposure therapy via a telemedicine-based virtual reality clinic (Doxy.me VR) vs. standard telemental health (TMH) to adults with intense fear of dogs, snakes, and/or spiders.
Secondary Objective(s)/Purposes	Preliminarily examine the efficacy of using Doxy.me VR vs. TMH in reducing phobia severity.
Research Intervention(s)	Exposure Therapy
ClinicalTrials.gov NCT #	Registration on clinicaltrials.gov is pending
Study Population	Adults (≥ 18 years old) with intense fear of dogs, snakes, and/or spiders.
Sample Size	30
Study Duration for individual subjects	In total, participants will spend approximately 38 hours over 13 study visits (12 Therapy and 1 Baseline Assessment) engaging in study procedures over the course of three months.
Study Specific Abbreviations/ Definitions	telemedicine-based virtual reality clinic (Doxy.me VR); standard telemental health (TMH); Virtual Reality (VR); Cognitive Behavioral Therapy (CBT)

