2.0 Objectives

2.1 Primary Objective: Assess the feasibility of conducting a randomized controlled efficacy trial comparing the delivery of exposure therapy via a telemedicine-based virtual reality clinic (Doxy.me VR) vs. standard telemental health (TMH) to adults with intense fear of dogs, snakes, and/or spiders.

Secondary Objective: Preliminarily examine the efficacy of using Doxy.me VR vs. TMH in reducing phobia severity.

2.2 This is a feasibility trial and not powered for hypothesis testing.

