5.0 Procedures Involved

This study will use feasibility randomized controlled efficacy trial design. This single-site trial will include up to 60 adults with self-reported fear of dogs, snakes, and/or spiders who will be randomly assigned via the REDCap Randomization Module using a 1:1 allocation ratio to receive 12 sessions of exposure therapy over the course of 3 months via standard telemental health (TMH; $n=15$) vs. Doxy.me VR ($n=15$), a telemedicine-based virtual reality clinic. Participants randomized to the Doxy.me group will be provided with Quest 2 VR headsets with the Doxy.me VR application pre-loaded to the device. This VR clinic is a standalone app currently available on Quest 2 headsets via

invite only. The app is designed for a therapist to meet with a client in a private, comfortable VR clinic office. To join each other in VR, the therapist selects a room code and provides that code to their client, who joins by entering that code into the app. While in the same VR room, the therapist and client can interact by speaking with each other in immersive VR. Therapists can also spawn a variety of small animals such as dogs, snakes, and spiders for use in treating specific phobias. Therapists can browse, select, maneuver, remove, and choose animations for the animals to exhibit once made visible to the client.

Therapy sessions will be audio recorded and 20% will be observed by the PI to assess treatment fidelity. Primary clinical outcomes (i.e., phobia severity as measured by the SMSF) will be assessed at baseline and 3-months post-baseline. Intervention targets will include presence—assessed weekly via patient-report— and working alliance—assessed at mid- and post-treatment via study therapist- and patient-report. Benchmarks for feasibility will include enrolling up to 60 patients during months 1-9 of the trial (i.e., 3/month), 70% patient retention at 3-month follow-up, 70% of weekly self-report collected, and $\geq 80\%$ treatment fidelity.

5.2 Please select the methods that will be employed in this study (select all that apply):

 Audio/Video Recording	 Psychophysiological Recording
 Behavioral Interventions	 Record Review - Educational
 Behavioral Observations and Experimentations	 Record Review - Employee

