16.0 Data Management and Confidentiality

16.1 We will assess feasibility of the proposed trial methodology using the following benchmarks: 30 participants will be enrolled in months 1-9 of trial, 70% of participants will be retained at three-month follow-up, 70% of weekly self-report assessments will be completed, and we will reach 80% or greater treatment fidelity.

The small sample size prevents any conclusions about efficacy; however, Analysis of Covariance will be used to conduct a preliminary assessment of between-group differences in clinical outcomes while co-varying for pre-treatment scores. We also will conduct a preliminary examination of associations between study targets including therapeutic alliance and presence.

16.2 D.

We will use the following security measures to protect data sources:

1. Data collected during the trial will be securely stored in a HIPAA compliant USF REDCap database, including informed consent documents, questionnaire data, and session notes.
2. Consent forms and de-identified data will be downloaded and stored in a secure HIPAA compliant Box folder.
3. All research data exported from REDCap will include ID numbers only.
4. Audio recordings will be stored in a secure HIPAA compliant USF Box folder.
5. Only IRB-approved and trained study personnel will have access to the REDCap project and box folder.
6. Computers, programs, and box folders containing data will be password-protected to prohibit unauthorized access.
7. The codes that link the name of the participant and the study ID will be kept confidential in REDCap along with other identifiers including first name, last name, full date of birth, address, email address, and cell phone number.
8. We have obtained a Certificate of Confidentiality from the National Institutes of Health so that we cannot be forced to disclose information that may identify participants, even by a court subpoena, in any federal, state, or local civil, criminal, administrative, legislative, or other proceedings.

16.3 We will use the following quality assurance measures for subject recruitment, enrollment, enrollment targets, and for the validity and integrity of the data:

1. study staff will complete and maintain up-to-date CITI and GCP training

2. study staff will be trained and supervised weekly by the PI
3. Standard Operating Procedures (SOPs) and study checklists will be used to train study staff and ensure fidelity to the study protocol

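### The protocol uses 30 and 60 for different populations, so the enrolment benchmark of its primary feasibility objective has no single value

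*Protocol*

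**What the plan says.** Five statements in the protocol bear on the size of the trial.

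- Section 1.1 gives "Sample Size 30" and does not say whether these are enrolled, randomised or completing participants.
- Section 5.0, design paragraph: "This single-site trial will include up to 60 adults with self-reported fear of dogs, snakes, and/or spiders who will be randomly assigned". The same sentence specifies 1:1 allocation and arms of 15 and 15.
- Section 5.0, benchmarks: "enrolling up to 60 patients during months 1-9 of the trial (i.e., 3/month"), together with 70% retention at three months.
- Section 11.1: "We aim to complete treatment with and obtain post-treatment assessment data from a total of 30 participants", 15 in each arm. Up to 60 may be enrolled, as needed, to cover screening failures, withdrawals and dropouts.
- Section 16.1 sets the enrolment benchmark at 30 enrolled in months 1-9 and adds that "70% of participants will be retained at three-month follow-up".

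On timing, the consent and baseline part of Section 5.0 places randomisation after the final eligibility decision. Section 2.2 states: "This is a feasibility trial and not powered for hypothesis testing". There is therefore no power-based sample size to reproduce.

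**The concern.** The primary objective is to judge feasibility, and enrolment and retention are two of the four benchmarks by which it will be judged. Each needs a fixed target and a fixed denominator.

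As written, 30 is an enrolment count in Section 16.1 and a completer count in Section 11.1. Sixty is a number randomised in one sentence of Section 5.0 and an enrolment ceiling in Section 11.1. The enrolment benchmark is up to 60 in one place and 30 in another, and an up-to figure sets no minimum that could be missed. Two readers could look at the same final counts and disagree on whether the trial succeeded.

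There is a second, smaller consequence. Section 11.1 lets enrolment continue as needed to offset dropout, so the number randomised depends on attrition. Unless retention is counted over everyone randomised, reaching 30 completers could be reported without showing how many were lost on the way.

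**Working it through.** **Inputs** (all from the protocol): arms 15 and 15, up to 60 randomised, 3 per month over months 1-9, 70% retention (Section 5.0); 30 completers and a ceiling of 60 enrolled (Section 11.1); 30 enrolled and 70% retention (Section 16.1).

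**1. Arms against number randomised (Section 5.0).** 15 + 15 = 30, not 60.

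**2. Monthly rate against enrolment benchmark.**
- 3 per month × 9 months = 27.
- 60 / 9 = 6.7 per month; 30 / 9 = 3.3 per month.

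The stated rate is far from what 60 needs. It is close to what 30 needs, and looks like a rounded figure for 30.

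**3. Section 16.1 against Section 11.1.** Expected completers = number randomised × retention. Taking the 30 enrolled as 30 randomised, 30 × 0.70 = 21, and the shortfall against Section 11.1 is 30 − 21 = 9. If screening failures also count as enrolled, fewer than 30 are randomised and the shortfall is larger.

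**4. Number to randomise for 30 expected completers at 70%.** 30 / 0.70 = 42.9, so 43. Per arm, 15 / 0.70 = 21.4, so 22, or 44 in all; 44 × 0.70 = 30.8. If true retention is 70%, the binomial probability of at least 30 completers is 0.59 with 43 randomised and 0.67 with 44. Thirty is thus an expectation at that size, not an assured number.

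**5. Does Section 11.1 on its own conflict with 70% retention?** The ceiling of 60 includes screening failures, who are not randomised. With 60 enrolled and 43 or 44 randomised, 17 or 16 would be screening failures (28% or 27%), and 30 completers would be about 70% of those randomised. The protocol gives no screening-failure share, so a range is shown as an assumption:

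| Assumed screening-failure share | Randomised out of 60 | Retention at which 30 complete |
|---|---|---|
| 10% | 54 | 30/54 = 56% |
| 20% | 48 | 30/48 = 63% |
| 30% | 42 | 30/42 = 71% |
| 40% | 36 | 30/36 = 83% |

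So Section 11.1 can be reconciled with 70%. The conflict arises when it is set beside Section 16.1 and beside the statement in Section 5.0 that the up-to-60 are randomly assigned.

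**6. Why the retention denominator matters.** Taking the 20% row as an illustration, randomising 48 to obtain 30 completers meets the Section 11.1 aim but gives 62.5% retention, below the benchmark. Only a denominator of all 48 shows this.

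**The case against.** The best defence is that the plan makes sense once the terms are separated: 60 is a ceiling on people enrolled, some fail screening, some drop out, and about 30 finish. Step 5 shows that this works at 70% retention. It clears Section 11.1, but not the rest. Section 5.0 says the up-to-60 are randomised, although screening failures cannot be, and Section 16.1 still sets 30 as the number enrolled.

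It can also be said that 70% is a feasibility benchmark and not a planned attrition rate. That is correct. The figures of 21 and 43-44 describe what happens when the benchmark is just met; they are not forecasts. The trial is not powered for hypothesis tests, and Section 16.1 disclaims conclusions about efficacy, so no confirmatory inference is at risk.

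A reader might be tempted to go further in four ways, none of which the protocol supports.

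- **That the design implies 50% retention** (30 of 60). This holds only if all 60 are randomised. Section 11.1 makes 60 a ceiling that includes screening failures.
- **That 30 completers are all but impossible.** This assumes that exactly 30 are randomised with no further enrolment, which Section 11.1 does not plan.
- **That the analysis of covariance is confined to completers.** No section says so. Section 13.2 has staff attempt assessments in people who partially withdraw, and analysis sets are commonly left to a statistical analysis plan.
- **That allocation would be steered to reach 15 completers per arm.** The 15 per arm is stated as an aim, and allocation is 1:1 through the REDCap module.

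**Conclusion.** The inconsistency is real and affects figures on which the primary objective depends. Section 5.0 contradicts itself on the number randomised (up to 60 against 15 + 15 = 30) and on accrual (up to 60 against 3 × 9 = 27). Sections 5.0 and 16.1 give different enrolment benchmarks, and Sections 11.1 and 16.1 use 30 for different populations. The Section 16.1 enrolment and retention benchmarks can both be met with 21 completers, nine short of the Section 11.1 aim.

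The figure of 21 assumes that the 30 enrolled are all randomised and that retention is exactly 70%. The 43 (44 for equal arms) needed for 30 expected completers rests on the same retention. Section 11.1 taken alone is not in error. Concealed attrition is a possibility that the wording leaves open, and not something the protocol plans.

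**What to change.** State three separate numbers and use them consistently in Sections 1.1, 5.0, 11.1 and 16.1: consented or enrolled (ceiling 60), randomised per arm, and expected with post-treatment data. Two versions are coherent at 70% retention:

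- 30 randomised (15:15), with about 21 expected to give post-treatment data; or
- 44 randomised (22:22), with about 30 expected. Within a ceiling of 60 enrolled this leaves room for 16 screening failures, so the assumed screening-failure share should be stated.

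Set one enrolment benchmark, say whether it counts enrolled or randomised people, and give a monthly rate that matches it. If it counts randomised people over nine months, 30 needs 3.3 per month and 44 needs 44 / 9 = 4.9.

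Define retention over all randomised participants, so that people enrolled to offset dropout cannot hide attrition. Describe 15 completers per arm, if kept, as an expectation and not a quota.

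The cost is wording; neither version goes beyond the existing ceiling of 60. If 30 randomised is kept, the stated completer figure falls from 30 to about 21. If 44 is chosen, the recruitment rate must rise above the stated 3 per month.

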12.0 Recruitment Methods

12.1 Potential participants will be identified through Clinical Connection, Research Match, Facebook ads, and distributing flyers on University of South Florida campus.

Clinical Connection is a national clinical trial participant recruiter. Clinical Connection matches potential study participants with clinical trials in a 50-mile radius of their location. Study sites post listings for clinical trials and potential participants are notified that a new clinical trial has been posted if they are signed up for alerts. Study sites can also send direct emails to potential participants every 30 days. Interested potential participants review the clinical trial description and fill out a contact form. The study site receives an email with the potential participant's contact information and reaches out to them directly. Clinical Connection also posts paid advertisements for clinical trials on popular search engines. The study team will contact Clinical Connection referrals within one business day of submission to provide study information, assess eligibility, obtain

informed consent from patients, and assist participant in completing baseline assessments. IRB approval is required prior to launching the study on Clinical Connection. There are four documents in Local Site Documents related to Clinical Connection: Clinical Connection Advertisement Example, Clinical Connection Research Site Profile Example, Clinical Connection Research Site Profile Text, and Clinical Connection Advertisement Text. These documents provide examples of posted studies and the text we intend to use on the advertisements for this study.

ResearchMatch connects volunteers with researchers. Volunteers and researchers register for the site, and researchers can contact deidentified volunteers with information about their study. Volunteers registered for the site will be contacted through direct message on ResearchMatch. If a ResearchMatch volunteer expresses interest, the study team will contact them within one business day to provide study information, assess eligibility, obtain informed consent from patients, and assist participant in completing baseline assessments. At present, there are 80 English-speaking adults with a phobia diagnosis registered on Research Match.

Facebook advertisements will target relevant Facebook users. Potential participants will complete a contact form. As with the previous recruitment methods, potential participants will be contacted by the study team within one business day.

Distributing Flyers on USF Campus will involve placing flyers at USF Counseling Center, USF Student Health Center, and areas throughout campus where students congregate. As with the previous recruitment methods, potential participants will be contacted by the study team within one business day.

Distributing Flyers Off-Campus will involve placing flyers in community centers and businesses where people congregate. Examples include but are not limited to public libraries, coffee shops, recreation centers. As with the previous recruitment methods, potential participants will be contacted by the study team within one business day.

Distributing Flyers in Online Communities will involve posting advertisements in online mental health forums and groups including but not limited to Reddit. As with the previous recruitment methods, potential participants will be contacted by the study team within one business day.

12.2

 Email	 Record Review
 Flyer	 SONA
 Letter	 ResearchMatch (must upload HRP-500 template)
 News Advertisement	 Other: Clinical Connection
 Online/Social Media Advertisement	

12.3 N/A

13.0 Withdrawal of Subjects

13.1 Anticipated circumstances under which participants will be withdrawn from the research without their consent include the event that they:

1. Begin participating in ongoing mental health therapy from a non-study therapist
2. Have changes to psychotropic medication use
3. Begin to report active suicidal and/or homicidal intent or plan
4. Begin to report active auditory, visual, and/or tactile hallucinations
5. Begin to report the occurrence of photosensitive epilepsy or seizures
6. Moves out of the State of Florida during the study period

13.2 If subjects completely withdraw from the research, study staff will attempt to provide them with a referral to a therapist in their area. If subjects partially withdraw from the research, study staff will attempt to administer mid- and post-treatment assessments. Subjects will be given the option to completely withdraw from the study including withdrawing previously collected data.

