8.0 Study Timelines

8.1 The study timeline with estimated visits and their accompanying durations can be viewed in Figure 2. Study Schema and Schedule of Events. Participants will participate in a ≤60-minute initial consent and baseline assessment visit (Visit 1). They will then participate in 12 ≤60-minute therapy sessions (Visits 2-13) and up to 6, ~30-minute homework assignments per week over 12 weeks. Participants will also participate in 20-minute mid- and post-treatment assessments, which will occur during Visits 7 and 13, respectively. In total, participants will spend approximately 38 hours over 13 study visits (i.e., Baseline + 12 Therapy Sessions) engaging in study procedures over the course of three months.

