9.0 Inclusion and Exclusion Criteria

9.1 In order to be eligible to participate in this study, an individual must meet all of the following criteria:

1. Is an adult ≥ 18 years old
2. Has a self-reported fear of dogs, snakes, and/or spiders
3. Indicates *Subthreshold* or *Present* Specific Phobia symptoms as determined by the study therapist via administration of the Diagnostic Assessment Research Tool (DART) Specific Phobia Module
4. Has access to the internet AND a computer OR smartphone with video conferencing capabilities
5. Will reside in the state of Florida for the duration of the study

9.2 An individual who meets any of the following criteria will be excluded from participation in this study:

1. Is participating in ongoing mental health therapy from a non-study therapist
2. Has had changes to psychotropic medication use within six weeks preceding enrollment in the trial
3. Reports active suicidal and/or homicidal intent or plan as determined by the study therapist via administration of the Diagnostic Assessment Research Tool (DART) Risk Assessment Module

4. Reports active auditory, visual, and/or tactile hallucinations via the Diagnostic Assessment Research Tool (DART) Psychosis Module screening question
5. Reports having a diagnosis of photosensitive epilepsy by a medical doctor or a history of experiencing seizures that they believe were caused by photosensitivity

9.3 An individual who meets any of the following criteria will become ineligible to continue on the study after enrollment:

1. Begins participating in ongoing mental health therapy from a non-study therapist
2. Has changes to psychotropic medication use
3. Does not indicate *Subthreshold* or *Present* Specific Phobia symptoms as determined by the study therapist via administration of the Diagnostic Assessment Research Tool (DART) Specific Phobia Module
4. Reports active suicidal and/or homicidal intent or plan as determined by the study therapist via administration of the Diagnostic Assessment Research Tool (DART) Risk Assessment Module
5. Moves out of the State of Florida during the study period

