19.0 Compensation for Research-Related Injury

19.1 N/A

20.0 Subject Costs and Compensation

20.1 Patients who participate in this study will have internet and smartphone access, so we anticipate that they will have data and text message plans that will allow them to participate without any additional costs. However, there is the small risk that some participants may exceed their monthly data or text message limits during this study resulting in additional costs, for which they will be responsible. This risk will be discussed during the informed consent process.

20.2 If you will provide compensation to subjects, select all that apply:

 No Compensation	 Tokens (pens, food items, etc.)
 Financial Compensation (cash, gift cards)	 Other
 Course Credit (i.e. extra credit, SONA points)	

Participants will receive a \$50 eGift card for completing the baseline assessment, \$50 eGift card for completing the 6th therapy session, and a \$50 e-gift card for completing the 3-month follow-up assessment. There will be no partial compensation for partially completing either assessment.

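### Sections 13.1 and 9.3 remove participants from the research rather than from study treatment only, and 13.2 does not clearly keep them in 3-month assessment

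*Protocol*

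**What the plan says.** Protocol section 13.1 introduces its list with "Anticipated circumstances under which participants will be withdrawn from the research without their consent include the event that they". The triggers are outside therapy, a change in psychotropic medication, suicidal or homicidal intent or plan, hallucinations, photosensitive epilepsy or seizures, and moving out of Florida.

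Section 9.3 states that people meeting an overlapping list "will become ineligible to continue on the study after enrollment". It omits hallucinations and seizures, and adds (item 3) not showing subthreshold or present phobia symptoms on the diagnostic interview.

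Section 13.2 describes two outcomes. Those who withdraw completely are offered a referral. For the others: "If subjects partially withdraw from the research, study staff will attempt to administer mid- and post-treatment assessments".

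Other relevant statements:
- Section 5.0: phobia severity "will be assessed at baseline and 3-months post-baseline".
- Section 8.1: "mid- and post-treatment assessments, which will occur during Visits 7 and 13, respectively". Visit 13 is the last therapy session.
- Section 16.1: the benchmark is that "70% of participants will be retained at three-month follow-up".
- Section 11.1: "We will enroll up to 60 participants in the trial as needed to account for screen fails, withdrawals, and drops".
- Section 20.2: a separate $50 "e-gift card for completing the 3-month follow-up assessment".

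**The concern.** Stopping study treatment and stopping data collection are different decisions, and sections 13.1 and 9.3 do not separate them. Two of the triggers, outside therapy and a medication change, occur after randomization and can plausibly follow a poor response. If these people leave the research altogether, the missing 3-month scores may be related to outcome. Enrolling more people under section 11.1 restores the count but does not replace those scores.

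Two things are at stake. The first is the 70% retention benchmark, which serves the primary feasibility objective: someone willing to be assessed could count as lost because of the trial's own rule. The second is the preliminary ANCOVA of clinical outcomes in section 16.1, which would run without those people. This is a rule about what data are collected, so a statistical analysis plan cannot repair it afterwards.

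**Working it through.** **Reading the sections together**

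1. Sections 13.1 and 9.3 refer to the research and the study. Neither limits removal to treatment.
2. Section 13.2 words both complete and partial withdrawal as something the subject does. It neither places staff-removed people in the partial route nor excludes them from it. The wording of 13.1 points towards complete withdrawal.
3. Under 8.1 the post-treatment assessment takes place during the last therapy visit, so a person taken off treatment has no scheduled occasion for it unless 13.2 supplies one.
4. The means to assess them exist: the outcome is timed from baseline (5.0), questionnaires are completed in REDCap with staff present by videoconference (5.0), and the 3-month assessment is paid for separately (20.2).

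**Effect on the retention benchmark**

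The protocol states no removal or dropout rate, so there is no figure to reproduce and every rate below is an assumption. Let L be other loss and r the removal rate among the rest, with nobody assessed after removal. Retention is (1 − L)(1 − r), and the chance of meeting the benchmark is P(Bin(n, (1 − L)(1 − r)) ≥ 0.7n). For n = 30 (section 16.1) this needs 21 retained; for n = 60 (the section 11.1 ceiling) it needs 42.

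| n, L | r = 0 | 1% | 2% | 3% | 5% | 10% |
|---|---|---|---|---|---|---|
| 30, 15% | 0.990 | 0.986 | 0.980 | 0.972 | 0.951 | 0.854 |
| 30, 20% | 0.939 | 0.924 | 0.906 | 0.886 | 0.838 | 0.681 |
| 30, 25% | 0.803 | 0.775 | 0.745 | 0.714 | 0.647 | 0.470 |
| 60, 20% | 0.978 | 0.968 | 0.955 | 0.937 | 0.890 | 0.693 |

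If half of those removed still give a 3-month score (n = 30, L = 20%), retention is 0.8 × (1 − r/2):
- r = 3%: 0.788, and the chance rises from 0.886 to 0.915.
- r = 5%: 0.780, from 0.838 to 0.896.
- r = 10%: 0.760, from 0.681 to 0.838.

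**Effect on the efficacy comparison**

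Suppose one arm of 15 has one or two more removals than the other, and removed people differ from the rest by 0.5 to 1.0 SD (assumption). The shift in the difference is (extra removals / 15) × gap, from 1/15 × 0.5 = 0.03 SD to 2/15 × 1.0 = 0.13 SD. It is zero if removals and gaps are equal across arms.

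The ANCOVA 95% half-width with 15 per arm is t(0.975, 27) × √(2/15) × √(1 − ρ²), where ρ is the baseline-to-outcome correlation (assumed). With t = 2.052 this is 0.75 SD at ρ = 0 and 0.54 SD at ρ = 0.7. The possible shift lies well inside the interval.

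**The case against.** The strongest reply is that this is an ambiguity and not an exclusion. Section 13.2 follows the 13.1 list under the same heading, already contains an off-treatment assessment route, and does not bar staff-removed people from it. Figure 2, the schedule of events, is not visible and might show such an assessment; the operating procedures mentioned in section 16.3 might also cover it. This stands as a limit on the point. A reader might infer that the protocol forbids assessing removed participants. It does not say that; it leaves the matter unclear, with wording that leans the wrong way.

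Second, counting a removed person as not retained is a legitimate feasibility result. That also stands. It is a reason to report removals next to retention, not to redefine retention.

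Third, the size rests on assumed rates. At 1–3% removal, 30 × 0.8 × r gives only 0.24 to 0.72 people, and nothing in the document supports 5% or 10%. Section 9.2 already excludes people in outside therapy or with a medication change in the six weeks before enrolment. This stands too.

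Fourth, rewording every trigger would reach further than needed. The safety triggers have clinical reasons, and the protocol does not explain the Florida rule, so out-of-state contact may not be acceptable. The change should be confined accordingly.

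A reader might also infer from 9.3 item 3 that people are removed once their phobia resolves, which would be selection on the outcome. The visible text does not support that: item 3 is absent from 13.1, no repeat of the diagnostic interview during treatment is described, and it reads as an eligibility failure at baseline.

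**Conclusion.** The point holds as a minor correction to a data-collection rule. Sections 13.1 and 9.3 take people out of the research after events that may be related to outcome, and 13.2 does not clearly bring them back for the 3-month score.

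The consequence is probably small. With 30 enrolled and 20% other loss, the chance of meeting the benchmark drops by about 2 to 5 percentage points at 1–3% removal (0.939 to 0.924 and 0.886). It becomes material only from about 5% removal, where the drop is about 10 points. All of these rates are assumed.

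A reader might go further and infer that the efficacy comparison is materially biased, or biased in favour of one arm. The documents do not support that: the direction is unknown, the shift is small against the interval, and sections 2.2 and 16.1 disclaim power and any conclusion about efficacy.

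**What to change.** - **13.1 items 1–2 and 9.3 items 1–2** (outside therapy, medication change): reword so that the participant is *withdrawn from study treatment*. Leave the wording of the safety and relocation triggers as it is.
- **13.2**: add one sentence. Participants removed under 13.1 or 9.3, other than 9.3 item 3, are handled as partial withdrawals and asked to complete the mid- and post-treatment questionnaires remotely, the latter at 3 months post-baseline, unless they refuse, the study therapist judges it clinically inappropriate, or contact outside Florida is not permitted.
- **Recording and reporting**: record the date and reason of each removal, and report removals by arm and reason alongside the 70% retention figure.
- **Unchanged**: the right to withdraw completely, including data already collected, and the assessment timing for everyone else.

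The cost is a few sentences of protocol text and a few staff contacts. With 30 enrolled, 20% other loss and 1–10% removal (assumptions), 30 × 0.8 × r gives 0.24 to 2.4 people removed; at $50 each, that is $12 to $120 in gift cards. The downside is that some of the added scores will include the effect of outside therapy or a medication change. The recorded date and reason allow those scores to be flagged.
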